## 13.2 POPULATION PHARMACOKINETIC MODELING

The sparse plasma samples collected during Parts A and B will be used to refine the existing population PK model for SUBLOCADE developed from the combined analysis of the multiple-ascending-dose study (RB-US-12-0005) and the 2 Phase III studies (RB-US-13-0001 and RB-US-13-0003) (modeling report, IND-6000-M05). The purpose is to characterize the long-term decrease in buprenorphine plasma concentration following discontinuation of SUBLOCADE treatment.

The final model will be used to derive population predictions for the 2 dosing regimens of SUBLOCADE and to derive endpoints such as the distribution of times for which buprenorphine plasma concentrations are above the lower limit of quantification.

### 13.2.1 Existing Population Pharmacokinetic Model for SUBLOCADE

The PK of buprenorphine following repeated SC injections of SUBLOCADE has been well characterized using non-linear mixed effects modeling with the combined analysis of 3 clinical studies: RB-US-12-0005 (Phase IIA multiple-ascending-dose study), RB-US-13-0001 (Phase III pivotal efficacy study) and RB-US-13-0003 (Phase III long-term safety and tolerability study). All studies were conducted in subjects with opioid use disorder following induction and dose stabilization with sublingual buprenorphine tablet or film.

[figure not shown]
As shown in Figure 2, the disposition model consisted of a 2-compartment model with first-order elimination. The absorption of buprenorphine from the SC injection site was described by a dual absorption model including (i) a first-order absorption rate constant ( $k_{24}$ ) to characterize the rapid absorption process associated with the early peak, and (ii) a transit compartment absorption model (rate constants  $k_{36}$  and  $k_{64}$ ) to mimic the slow delivery of buprenorphine from the SC depot. The fraction of SUBLOCADE absorbed via the slow (F3) or fast (F2) process was estimated.

A first-order rate constant ( $k_{14}$ ) was selected to model the absorption of SL buprenorphine. The relative bioavailability of SUBUTEX (used in Study RB-US-12-0005) vs. SUBLOCADE (F1) was estimated. Changes in bioavailability and absorption rate for

SUBOXONE film (used in Phase III studies) relative to SUBUTEX tablet were also estimated.

The model was parameterized in terms of clearances and volumes. Based on prior knowledge and for mechanistic reasons, clearances and volumes of distribution were allometrically scaled by body weight using the well-established power model and exponents of 0.75 for clearances and 1 for volumes.

**Figure 2**      **Structural Model for Buprenorphine After Sublingual and Subcutaneous Administration from the Combined Population Pharmacokinetic Analysis of Studies RB-US-12-0005, RB-US-13-0001 and RB-US-13-0003**

See Table 1 for the definition of PK parameters

Source: INDV-6000-M04 Figure 1

The population PK model was developed in 2 steps using NONMEM software version 7.3.0:

- Step 1: Development of base and final covariate models from the joint analysis of Studies RB-US-12-0005 and RB-US-13-0001 (total of 17 235 observations in 507 subjects)

- Step 2: Prediction of Study RB-US-13-0003 and model refinement using the totality of the data (total of 19 686 observations in 570 subjects).

Additional information on model building, model parameter estimates and model evaluation can be found in the PK modeling reports INDV-6000-M04 (Step 1) and INDV-6000-M05 (Step 2).

Overall, the model provided a very good description of the plasma concentration-time profiles following SC injection of SUBLOCADE at each dose level, across the 3 studies. Two statistically significant covariates were identified during the covariate analysis: BMI and sex. Sex had a significant effect on the slow absorption of buprenorphine from the SC depot (k36) but this effect was marginal. Body mass index was also found to affect SC absorption (k24) and the apparent clearance of buprenorphine, with higher buprenorphine peak levels in subjects with a lower BMI.

Model parameter estimates are displayed in Table 1.

**Table 1 Estimates of Previous Population Pharmacokinetic Model (Combined Analysis of Phase II/III Data)**

Parameter	Description	Estimate (RSE%)		Variance (RSE%)		IIV (%)
k14	Sublingual absorption rate constant (h  )	1.17	(FIXED)	0.190	(FIXED)	45.7
k24	Fast absorption rate constant from SC depot (h  )	0.0276	(5.1)	0.654	(16)	96.1
k36	Slow absorption rate constant from SC depot (h  )	0.00362	(7.4)	1.54	(11)	191
k64	Rate constant from Transit compartment to Central (h  )	0.000510	(3.7)	0.432	(11)	73.5
CL	SUBLOCADE apparent elimination clearance (L/h)	52.0	(1.5)	0.0871	(9.5)	30.2
V4	SUBLOCADE apparent volume of central compartment (L)	433	(27)	0.647	(12)	95.4
Q	SUBLOCADE apparent distribution clearance (L/h)	79.5	(FIXED)	0.334	(FIXED)	63.0
V5	SUBLOCADE apparent volume of peripheral compartment (L)	1110	(FIXED)	0.941	(FIXED)	125
F1	Relative bioavailability of SUBUTEX compared to SUBLOCADE	0.185	(FIXED)	0.195	(FIXED)	46.4
F2	Fraction of SUBLOCADE dose absorbed by fast process	0.0679	(2.2)	0.204	(11)	NA #
FRK14	Relative change in k14 for SUBUXONE compared to SUBUTEX	0.650	(11)	NA		NA
FRF1	Relative change in F1 for SUBUXONE compared to SUBUTEX	1.47	(3.5)	NA		NA
F1DOSE	Relative change in F1 for dose ≥ 16mg compared to dose < 16mg	0.765	(FIXED)	NA		NA
θ BMI (CL)	Power coefficient for BMI on CL/F	-0.364	(21)	NA		NA
θ BMI (k24)	Power coefficient for BMI on k24	-1.32	(14)	NA		NA
θ SEX (k36)	Fractional increase in k36 for females	0.0313	(282)	NA		NA
Add	Additive residual error (ng/mL)	0.0373	(14)	NA		NA
Prop	Proportional residual error	0.190	(0.66)	NA		NA

IIV=interindividual variability calculated as  $100 \times \sqrt{\exp(\omega^2) - 1}$ , where  $\omega^2$  is the variance of related subject-specific random effect; NA=not applicable; RSE=relative standard error; # logit-normal distribution.

Source: INDV-6000-M05 Table 5

### 13.2.2 Dataset Preparation

Buprenorphine plasma concentration data collected in Parts A and B will be merged with the previous NONMEM dataset that was used to develop the population model presented in Section 13.2.1.

R software version 3.4.3 or older will be used for data inspection and for the preparation of the input datafile for the population PK analysis in NONMEM. This will involve obtaining the required study variables from the primary data source for the current and previous studies, calculating the elapsed time from the last SUBLOCADE dose in Study RB-US-13-0003 or Study INDV-6000-301, and merging with the previous dataset combining Phase II/III data. All R codes related to data preparation, identification of potential outliers, and exploratory graphical analysis will be adequately commented for ease of use.

The NONMEM input file will be formatted as a comma separated (.csv) file and will include the following information: subject unique identification number, dosing information, actual sampling times, measured buprenorphine plasma concentrations, demographics (e.g., sex, age, weight, body mass index [BMI], race), study identification number, and flags for potential outliers and concentrations below the LLOQ.

Plasma concentrations below the LLOQ in the current study will be included in the analysis and will be handled using appropriate likelihood-based methodology.

Plasma concentrations associated with the reported use of illicit buprenorphine at the visit or the use of prescribed buprenorphine within 3 weeks of the visit (Part B – Visits 2 and 3) will be flagged as outliers, and although listed in the NONMEM dataset, will not be used for the population PK analysis.

### 13.2.3 Handling of Outliers

An outlier is defined as an aberrant observation that significantly deviates from the rest of the observations in a particular individual and does not refer to a subject as an outlier. The proportion of outliers in a dataset should be low and such points might be excluded from the analysis given the potential for these observations to impact the convergence and/or parameter estimates (i.e., which may cause a bias) (FDA Guidance, February 1999).

Outlier detection will be based on the visual inspection of individual and pooled data profiles and based on documented information such as the reported use of buprenorphine at the visit or the use of illicit or prescribed buprenorphine prior to the visit.

## 13.2.4 Population Pharmacokinetic Modeling

The criteria used in selecting the most appropriate models will be based on individual goodness-of-fit plots (e.g., DV vs. IPRED, IWRES vs. IPRED), overall goodness-of-fit plots (e.g., DV vs. EPRED, EWRES vs. EPRED), change in objective function value (likelihood ratio test for nested models) and precision of parameter estimates.

### 13.2.4.1 Structural model

The structural model selected for the combined analysis of Phase II/III data (Figure 2) will be used in the present analysis. This model assumes that the slow release of buprenorphine from the SC depot can be adequately described by a transit compartment absorption model with first-order rate constants  $k_{36}$  and  $k_{64}$ . This model might be revised depending on goodness-of-fit plots for long-term exposure buprenorphine data in the current study.

### 13.2.4.2 Stochastic model

Individual PK parameters will be assumed to be log-normally distributed, except for the fraction of SC dose allocated to the fast absorption process for which a logit-normal distribution will be used. A combined proportional and additive error structure will be evaluated for the residual error. Alternate error models may be tested if this model is not considered adequate based on the inspection of individual weighted residuals.

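### A residual error shared with the Phase II/III data may be too large for the late Study 402 samples, and the plan has no run or diagnostic aimed at detecting this

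*SAP*

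**What the plan says.** SAP section 13.2.2 merges the Study 402 plasma concentrations with the previous NONMEM dataset, which section 13.2.1 describes as a "total of 19 686 observations in 570 subjects". Values below the LLOQ stay in through a likelihood-based method.

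On the error model, section 13.2.4.2 says: "A combined proportional and additive error structure will be evaluated for the residual error". It continues: "Alternate error models may be tested if this model is not considered adequate based on the inspection of individual weighted residuals". No error term specific to this study or its assay is mentioned, and no threshold is set for judging the residuals.

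Table 1 gives the previous estimates. The row beginning "Additive residual error (ng/mL" shows 0.0373 with an RSE of 14%, and "Proportional residual error" is 0.190. Section 13.2.4 lists the model-selection criteria: goodness-of-fit plots, change in objective function and parameter precision. Section 13.2.5 adds visual predictive checks. Section 13.2.6 derives the monthly percentage below the LLOQ and the time above it, without saying whether residual error is added to the simulated concentrations.

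**The concern.** Study 402 was set up to inform concentrations 12 to 36 months after the last injection. Part A gives about 60 samples and Part B at most 2 x 30, so at most about 120 new samples join 19,686 old ones. An additive error shared by all of them draws on mainly earlier, higher concentrations. If it is larger than the true error of the new low measurements, the fit gives those measurements too little weight.

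The stated trigger for trying another error model is poorly suited to this fault. An oversized SD makes late residuals too small rather than too large, and the new points would be 120/19,806 = 0.6% of the residuals plotted. What is at stake is the exploratory objective of refining long-term predictions, and the time-above-LLOQ figures that would support guidance to patients and physicians.

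**Working it through.** **Inputs (SAP Table 1).** Additive SD 0.0373 ng/mL (the unit shows it is an SD); proportional error 0.190. "Slow absorption rate constant from SC depot" (k36): 0.00362 per h, variance 1.54. "Rate constant from Transit compartment to Central" (k64): 0.000510 per h, variance 0.432. Apparent clearance: 52.0 L/h, variance 0.0871. F2: 0.0679, variance 0.204 on the logit scale. The regimens are those of section 13.2.6. Assumed: independent random effects, reference covariates, 28-day dosing, and plasma concentration equal to slow input rate divided by clearance. The LLOQ is not given and is varied.

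**Reproducing the plan's figures.** 100 x sqrt(exp(variance) - 1) gives 73.5% for k64, 191% for k36 and 30.2% for clearance, as in Table 1. ln 2 / 0.000510 = 1,359 h = 56.6 days, inside the 43 to 60 day half-life in Protocol section 1.2.

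**Where the additive term dominates.** Residual SD = sqrt(0.0373² + (0.19 C)²). The two parts are equal at 0.0373/0.19 = 0.196 ng/mL. Residual CV is 42% at 0.1 ng/mL, 77% at 0.05 and 187% at 0.02.

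**Where the samples are predicted to lie.**

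| Month | Typical, 6x300 mg (ng/mL) | Typical, 2x300+4x100 mg (ng/mL) | Share of subjects below 0.0373 ng/mL (6x300 / 2x300+4x100) |
|---|---|---|---|
| 12 | 0.11 | 0.048 | 31% / 41% |
| 18 | 0.012 | 0.005 | 58% / 68% |
| 24 | 0.0013 | 0.0005 | 76% / 84% |
| 36 | near 0 | near 0 | 93% / 96% |

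Twelve injections instead of six change this little: 12x300 mg gives 56%, 74% and 91% at months 18, 24 and 36.

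**How much information is lost.** Expected information on typical log k64 was computed for 60 subjects with one sample each, spread evenly over months 12 to 36 and censored at the LLOQ. The comparison is SD 0.0373 against an illustrative 0.005 ng/mL. Share kept = (SE at 0.005 / SE at 0.0373)².

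| Regimen, LLOQ (ng/mL) | SE at 0.0373 | SE at 0.005 | Kept overall | Kept at month 36 |
|---|---|---|---|---|
| 6x300, 0.01 | 0.133 | 0.110 | 68% | 0.34/0.83 = 41% |
| 2x300+4x100, 0.01 | 0.152 | 0.116 | 58% | 0.19/0.69 = 28% |
| 6x300, 0.05 | 0.134 | 0.125 | 87% | 0.33/0.51 = 65% |
| 2x300+4x100, 0.05 | 0.154 | 0.139 | 81% | 0.18/0.29 = 62% |

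With SD 0.0373, information per subject is 1.4 to 1.6 at month 12, against a maximum of 1/0.432 = 2.31. It falls to about 0.2 to 0.3 at month 36.

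**What could go unseen.** With SD 0.0373, a common unmodelled tail in 60 samples shifts the objective function by about 17 if it is 0.02 ng/mL, by 4.3 if 0.01 and by 1.1 if 0.005. If the true additive SD were 0.005, weighted residuals would have an SD of about 0.47 at 0.1 ng/mL, 0.28 at 0.05 and 0.17 at 0.02, instead of 1.

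**Residual error in the simulations.** For 6x300 mg at month 36, the share above the LLOQ without and with residual error (SD 0.0373) is 14.9% and 45.7% at 10 pg/mL, about 11% and 36% at 20, 6.0% and about 15% at 50, and about 3% and 4% at 100.

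**The case against.** The strongest reply is that the SAP does not carry 0.0373 ng/mL forward. Table 1 marks its carried-over constants as fixed; the additive error has an RSE instead, so it was estimated, and the pooled fit would estimate it again. An RSE of 14% is worth only about 1/(2 x 0.14²) = 26 observations of additive error, so the new samples could pull it down. If the true value for this study is 5 to 10 pg/mL (assumed), an approximate check puts the shared SD at about 28 to 32 pg/mL; a cruder approximation gives 7 to 28. This stands. It makes the losses above close to a worst case, but most of that range is still too large for the late tail.

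A reader might infer that the late data get almost no weight and the model can barely learn from the study. The documents' figures do not support that. The weight of a point at a given concentration is not its information on k64: the 12-month level moves strongly with k64, and low or below-LLOQ results rule out slow release. The check also leaves out each subject's earlier Phase III data.

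Other safeguards exist. Unusually narrow residuals are a visible misfit if someone looks at the low end, section 13.2.4.1 allows structural revision on the fit to the long-term data, and predictive checks could show over-wide late intervals. What remains is that none of these is required for Study 402 alone, and the only stated trigger for changing the error model is the residual plot.

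Nor does section 13.2.6 say that residual noise will be added; its reference to predicted concentrations can be read as excluding it. That part is mostly a request for clarification. Finally, the primary endpoint is a plot of observed concentrations and does not depend on this model.

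**Conclusion.** The point holds as a partial loss in the late tail. One shared additive error, if larger than the true error of the Study 402 assay at low concentrations, down-weights the samples from about month 18 onward. At worst it keeps about 58% to 87% of the information on k64 over the whole window and about 28% to 65% at month 36. Samples at months 12 to 18 remain informative, so it would be wrong to call the refined tail a pure extrapolation from the earlier studies.

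This rests on assumptions the documents cannot settle: the LLOQ, the true additive SD in this study, independent random effects, and the simulated regimens standing in for the enrolled subjects. The effect is small if the LLOQ is 100 pg/mL or more. The change is worth making because it is cheap and a study-specific term looks estimable: with a true SD of 5 to 10 pg/mL and an LLOQ of 10 to 50 pg/mL, the approximate gain in objective function is about 16 to 67.

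**What to change.** - In SAP section 13.2.4.2, pre-specify one comparison run with an additive residual error specific to Study 402. If it cannot be estimated, fix it to the assay's precision at its LLOQ. Choose between this and the shared-error model by the criteria already in section 13.2.4, and state the plasma LLOQ.
- In sections 13.2.4 and 13.2.5, show weighted residuals and visual predictive checks for Study 402 alone.
- In section 13.2.6, derive time above the LLOQ and percentage below it from predictions without residual error, or report both versions with labels.

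The cost is SAP wording, one extra model run, and one or two parameters supported by about 60 to 120 partly censored observations, which may be imprecise. No change to data collection is needed.

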### 13.2.4.3 Covariate analysis

Covariate effects will be implemented as coded in the previous model (Table 1). No additional covariate analysis will be conducted.

## 13.2.5 Model evaluation

Model evaluation will be performed using visual predictive checks and standard goodness-of-fit plots (including DV vs. IPRED and DV vs. EPRED plots, EWRES vs EPRED and IWRES vs. IPRED plots).

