### **5.4 Part B Continuation Criterion**

Results on the quantitative UDS performed at Visit 1 will determine enrolment in Part B:

- Subjects who provide a quantifiable (i.e., positive) result for buprenorphine and/or norbuprenorphine and a non-quantifiable (i.e., negative) result for naloxone will continue into Part B of the study if Part B is still open to enrolment.
- Subjects who achieve negative results for both buprenorphine and norbuprenorphine quantitative UDS (irrespective of naloxone result) at Visit 1 will conclude their study participation, as will subjects who achieve a positive result for buprenorphine and/or norbuprenorphine and a positive result for naloxone on the quantitative UDS performed at Visit 1.

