### Part B

Results on the quantitative UDS performed at Visit 1 will determine enrolment in Part B: subjects who provide a quantifiable (i.e., positive) result for buprenorphine and/or norbuprenorphine and a non-quantifiable (i.e., negative) result for naloxone will meet continuation criteria to move on to Part B if Part B is still open to enrolment. Part B will consist of 2 visits, with 30 days ( $\pm 7$  days) apart between the two visits.

At each visit, the same assessments as in Part A will be performed. In addition, the subject will answer a question regarding his or her illicit use of buprenorphine within the last 14 days.

Part B may meet enrolment and be considered closed to new subjects while Part A is still open to enrolment. A schematic depicting the study design is presented in Figure 1.

[figure not shown]

Figure 1 Study Schematic

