## 15. DETERMINATION OF SAMPLE SIZE

The sample size is based on practical considerations and no statistical power is calculated. Approximately 60 subjects will be enrolled in Part A. This number of subjects is expected to provide a reasonable description of the distribution of plasma and urine concentration data in the overall population over the timeframe investigated (i.e., 12 to 36 months post the last SUBLOCADE injection), given the low-moderate interindividual variability (~30%) observed for SUBLOCADE PK in previous studies. The number of subjects to be enrolled in Part A is also limited by the availability of patients who received at least 2 SC injections of SUBLOCADE in Phase III studies and who remain in the time window targeted for enrolment in the current study. A maximum of 30 Part A subjects will proceed to Part B; it is anticipated that approximately 30 subjects will be sufficient to address the objectives for Part B. The final number of subjects will depend on results from quantitative buprenorphine UDS in Part A. Data will be reviewed on an ongoing basis.

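### Part B plasma samples are selected on a positive Visit 1 urine screen, but the planned predictive checks do not reproduce that selection, so a correct model can appear to under-predict the late data

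*SAP*

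**What the plan says.** Protocol 5.4 makes entry to Part B depend on the Visit 1 quantitative urine screen: "Subjects who provide a quantifiable (i.e., positive) result for buprenorphine and/or norbuprenorphine" continue, provided naloxone is negative and Part B is still open. The SAP introduction repeats the rule: "subjects who provide a quantifiable (i.e., positive) result for buprenorphine and/or norbuprenorphine and a non-quantifiable (i.e., negative) result for naloxone will meet continuation criteria".

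On numbers, SAP 15 states "Approximately 60 subjects will be enrolled in Part A" and "A maximum of 30 Part A subjects will proceed to Part B", over the window "12 to 36 months post the last SUBLOCADE injection".

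SAP 13.2 says "The sparse plasma samples collected during Parts A and B will be used to refine the existing population PK model". SAP 13.2.2 merges both parts with the earlier dataset and sets aside only samples linked to reported illicit or recent prescribed buprenorphine use. Values below the LLOQ are kept and handled through the likelihood.

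SAP 13.2.5 states "Model evaluation will be performed using visual predictive checks and standard goodness-of-fit plots", and lists DV vs IPRED, DV vs EPRED, EWRES vs EPRED and IWRES vs IPRED. It does not mention the urine rule, a split by visit, or any restriction of the simulated subjects. On the depot-release structure, SAP 13.2.4.1 adds "This model might be revised depending on goodness-of-fit plots for long-term exposure buprenorphine data in the current study".

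**The concern.** A standard visual predictive check simulates every virtual subject at every observed sampling time. At Visits 2 and 3 the real subjects are only those still urine-positive a month or two earlier, and these tend to be slow releasers. Urine is not part of the model, so the simulation does not reproduce this selection unless told to.

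Observed Part B values will then tend to lie above the simulated percentiles even when the model is right. That pattern looks like under-prediction of the tail. If it were read so when revision is considered under 13.2.4.1, the natural responses would be slower release or an added slow phase. Either would lengthen the predicted time above the LLOQ (SAP 13.2.6), which supports the guidance to patients and physicians described in Protocol 1.3. Earlier Phase II/III studies have no PK beyond 2 months after the last injection, so little other data could correct such a misreading.

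**Working it through.** **Inputs from the documents (SAP Table 1).** k36 = 0.00362 per h (variance 1.54); k64 = 0.000510 per h (variance 0.432); CL = 52.0 L/h (variance 0.0871); proportional error 0.190; additive error 0.0373 ng/mL.

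**Assumed, because the documents give no figure.** Plasma LLOQ 0.005–0.05 ng/mL; urine positivity at a level equivalent to 0.001–0.05 ng/mL in plasma; urine-to-plasma noise with log-SD 0.5–1.5; 2, 6 or 12 injections; equal mix of regimens; Visit 1 uniform over 12–36 (or 12–24) months.

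**1. Reproducing Table 1.** IIV = 100 × √(exp(variance) − 1). For k64, √(exp(0.432) − 1) = √0.540 = 0.735, which is the stated 73.5%. The same formula reproduces all nine IIV values in the table. The half-life ln 2 / 0.000510 = 1,359 h = 56.6 days falls within the 43 to 60 days in Protocol 1.2.

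**2. Why selection has leverage.** The log-SD of k64 is √0.432 = 0.657. At 24 months, t = 24 × 30.4 × 24 = 17,510 h, so k64·t = 8.93 for a typical subject. One SD slower, the rate is multiplied by exp(−0.657) = 0.518, giving 4.63. The exponential factor alone differs by exp(8.93 − 4.63) = exp(4.30), about 74-fold. Urine positivity at this distance therefore mostly sorts subjects by release rate.

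**3. Share of samples affected.** At most 30 × 2 = 60 Part B samples beside 60 × 1 = 60 from Part A, so up to 60 of 120. This is a ceiling: if 22% of 60 qualify, about 13 subjects give 26 samples.

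**4. Simulation with Table 1 as the truth.** The slow-release path was simulated with 120,000 subjects per scenario and no covariates. Each sample was compared with the unselected model median for the same month and regimen. Selected scenarios:

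| LLOQ (ng/mL) | Urine threshold (plasma equivalent) | Urine log-SD | Variation | Urine-positive | Visit 1 above median | Visits 2 / 3 above median | All pooled |
|---|---|---|---|---|---|---|---|
| 0.05 | 0.05 | 0.5 | – | 22% | 49.8% | 96.7 / 96.9% | 64.1% |
| 0.05 | 0.02 | 0.5 | – | 31% | 50.0% | 93.1 / 93.5% | 66.5% |
| 0.005 | 0.005 | 1.5 | – | 42% | 50.2% | 85.9 / 85.9% | 66.5% |
| 0.005 | 0.005 | 0.5 | 12–24 months | 59% | 50.0% | 81.1 / 81.3% | 65.6% |
| 0.005 | 0.005 | 0.5 | additive error 0.0373 kept | 43% | 49.8% | 68.4 / 66.5% | 58.0% |

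The pooled figure follows directly. In the first row, (60 × 0.498 + 26 × 0.968) / 86 = 55.0 / 86 = 64%. Without additive error the range over all scenarios is 81–97% for Part B and 64–68% pooled. Widening the urine threshold to 0.0005–0.05 ng/mL gives 76–99% for Part B. The share of Part B above the model's 95th percentile is 8–22%, against 5% at Visit 1.

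**5. Is selection the cause?** Applying the same Visit 1 urine rule to the simulated reference brings Part B back to 49–50% above the median in every scenario.

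**6. EPRED plots.** The SAP defines EPRED only as a Monte Carlo population prediction. If it is a mean (assumed), skewness leaves about 21% of unselected samples above it, against 33–81% of Part B.

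**7. Does the fit itself suffer?** A simplified one-exponential model was fitted by maximum likelihood, with values below the LLOQ censored, to 80 simulated studies of 60 subjects per scenario. Parts A and B together recover the mean rate constant (ratio to truth 0.99–1.02). Part B alone gives 0.57–0.68. Mean IWRES in Part B is 0.03–0.08. Conditioning each subject on its own Visit 1 plasma value brings the Visit 2 share above the predicted median to 51–63%, from 83–95% unconditioned.

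**The case against.** The strongest reply concerns the consequence. SAP 13.2.4 also selects models on individual plots, objective function and precision, and step 7 shows that the joint likelihood and IWRES are barely moved. A spurious slow phase should gain little support there. SAP 13.2.5 also names visual predictive checks separately from goodness-of-fit plots, while 13.2.4.1 refers only to the latter. This stands in large part. It does not clear the plan, because 13.2.4 lists DV vs EPRED and EWRES vs EPRED among its criteria, and these are population-level plots.

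Second, the size rests on quantities the documents do not give, and Protocol 1.3 says the plasma–urine correlation is unknown. This also stands. If urine status were unrelated to plasma concentration, the shift would vanish. A more sensitive urine assay, or entry on norbuprenorphine alone, weakens it. Where the model median is itself below the LLOQ, the shift shows as a higher share of quantifiable samples, not as a ratio of medians.

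Third, the SAP is silent; it does not say selection will be ignored, and its descriptive tables already separate Parts A and B. That is fair, and it makes the remedy a clarification.

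A reader might infer that structural decisions should therefore use Visit 1 data only. The documents do not support this. The synopsis gives Part B the task of showing whether PK profiles are consistent over time. Its samples are the only repeated late within-subject data, and they belong in the objective function.

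**Conclusion.** The point holds for the population-level diagnostics. With the Table 1 model exactly right, Part B samples will tend to lie above unselected predictions: roughly 76–99% above the model median without additive residual error, and about 67% with the old additive error kept in full (that figure is for a urine threshold of 0.005 ng/mL only). The direction was the same in every scenario. The size depends on the assumed LLOQ, urine threshold and urine–plasma link, and is smaller against a mean-type EPRED.

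A reader might go further and infer that the parameter estimates are biased, or that the release model will be revised in the wrong direction. Neither follows. Estimation from all visits with censored values is sound in the simplified check, the IPRED/IWRES plots are essentially unaffected, and other criteria also govern model choice. A mistaken revision is a risk that a few lines of SAP text would largely remove.

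**What to change.** In SAP 13.2.5, present the 12–36 month visual predictive check and the EPRED/EWRES plots separately for Visit 1, which is not selected on urine, and for Visits 2–3. For Visits 2–3, do one of the following:

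- keep only simulated subjects who meet a Visit 1 positivity rule, with a sensitivity range for the assumed urine–plasma link; or
- condition on the subject's Visit 1 plasma value, noting that this removes most but not all of the shift.

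In SAP 13.2.4.1, state that an upward shift of Part B in unconditioned population-level plots is not by itself grounds for structural revision. Keep all visits in estimation and in the objective-function comparison.

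The cost is SAP wording and one extra set of diagnostic plots. Each plot has fewer points, and the positivity-rule check rests on an assumed urine–plasma link. No new data are needed.
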